9.2 Subject Disposition

The number of maternal subjects screened will be presented, and the number of maternal subjects randomly assigned to receive trial treatment, completing the treatment period and completing the trial will be summarized by treatment group and analysis sets. The number of subjects providing data in the full analysis set (FAS) will be tabulated by treatment day. Reasons for discontinuation will be summarized by treatment group.

9.3 Protocol Deviations

Protocol deviations will be rated as either minor or major. Protocol deviations impacting the primary endpoint will be rated as major. Maternal subjects will be excluded from the per protocol (PP) analysis set from the day where the first major protocol deviations occurred and onwards. Data will not be excluded from the PP analysis set in case of minor protocol deviations. Major protocol deviations include but are not limited to the following:

- For a given treatment day:
 - Less than 5 milk expression attempts
 - Less than 80% compliance with intra-nasal administration of assigned treatment prior to milk expression

The Ferring clinical team will perform a blinded review of protocol deviations before declaration of clean file and lock of database. If the blinded review identifies serious unforeseen deviations deemed to impact the primary endpoint and affect the conclusions of the trial, these will also be rated as major deviations. A comprehensive list of major protocol deviations will be detailed and documented in the clean file document prior to database release. Major protocol deviations will be tabulated by treatment day and treatment group.

9.4 Analysis Sets

Analysis sets' definitions are based on the randomized maternal subject but will apply accordingly to the infant as well.

9.4.1 Intention-to-Treat Analysis Dataset

The Intention-to-Treat (ITT) analysis set is defined as all randomized maternal subjects.

9.4.2 Full Analysis Set

The FAS is defined as all randomized and exposed maternal subjects providing data on volume of MoM produced for at least 1 day after dosing initiation. Since this is a PoC trial, subjects will be analyzed according to actual treatment received.

9.4.3 Per Protocol Analysis Set

The PP analysis set will consist of data from all maternal subjects in the FAS without major protocol deviations (Section 9.3). Since this is a PoC trial, subjects will be analyzed according to actual treatment received.

9.4.4 Safety Analysis Set

The safety analysis set comprises all treated maternal subjects and infants and is analyzed according to the actual treatment received.

9.5 Trial Population

9.5.1 Demographics and Other Baseline Characteristics

Descriptive statistics of demographics and other baseline characteristics will be presented for all randomized maternal subjects by treatment group.

9.5.2 Medical History, Concomitant Medication and Other Safety Evaluations

Medical history will be coded using Medical Dictionary for Regulatory Activities (MedDRA) and will be summarized by treatment group. Prior and concomitant medications will be coded using the World Health Organization (WHO) Drug Dictionary and will be summarized by Anatomical Therapeutic Chemical Classification System (ATC) classification 1st level (alphabetically), ATC classification 2nd level (in decreasing order of frequency) and treatment group.

Reporting of other safety data prior to randomization and start of treatment is detailed together with reporting of safety data after randomization and start of treatment in Section 9.8.

9.6 Endpoint Assessments

9.6.1 General Considerations

Statistical analysis will be performed using SAS software Version 9.2 or later (SAS Institute, Inc, Cary, North Carolina) unless stated otherwise.

Analysis and Presentation of Primary and Secondary Endpoints

Results for the primary endpoint and secondary efficacy endpoints will be presented for both the FAS and the PP analysis sets. The primary endpoint and selected secondary efficacy endpoints will also be presented by gestational age group (<27 weeks and \geq 27 weeks).

Continuous variables will be summarized using the mean, standard deviation, median, minimum value and maximum value. Categorical variables will be summarized using frequency counts and percentages. All primary and secondary efficacy endpoints will be presented in data listings.

Treatment differences will (where appropriate) be presented with 95% two-sided confidence intervals and p-values corresponding to the statistical test of the hypothesis ‘equal effect’ against the alternative ‘different effect’. All statistical tests will be performed using a two-sided test at a 5% significance level, unless otherwise stated.

Multiplicity

Concerning the secondary efficacy endpoints, no formal adjustment for multiplicity will be utilized. Statistical significant results will be interpreted cautiously.

Missing Data

Missing data on the primary endpoint will not be imputed for the primary analysis. As this is a PoC trial, the interest is in assessing the difference in the amount of MoM expressed during treatment adherence. Furthermore, the repeated measures ANCOVA model is robust against dropouts under the assumption that the drop-out is not related to treatment. The reason for premature discontinuation will be compared between treatment groups. Sensitivity analyses examining the robustness of the primary analysis results with respect to the above missing data assumption will be carried out by imputing missing data under a missing-not-at-random (MNAR) assumption. The imputation will be carried out using the pattern mixture model with control based pattern imputation.³²

Missing values for the secondary endpoints will not be imputed.

9.6.2 Primary Endpoint

Primary Endpoint: Primary Analysis

The primary objective of this PoC trial is to evaluate the effect of merotocin on increasing milk production in women with preterm delivery. The primary endpoint of the trial is the volume of MoM produced over Days 1 to 14.

Repeated Measures ANCOVA Model:

The primary endpoint will be analyzed using a repeated measures ANCOVA with a general (unstructured) covariance matrix. The daily volume of MoM produced will be the dependent

variable. The model will include the baseline volume of MoM produced as covariate, with treatment group, treatment day, treatment-by-day interaction, and gestational age group (<27 weeks and \geq 27 weeks) as factors. The baseline volume of MoM produced is defined as the volume obtained at the 24-hour interval for eligibility during the observation period. The average treatment effect across treatment days and the within-day treatment effect will be reported along with the corresponding two-sided 95% confidence intervals and p-values.

The analyses based on the FAS will be considered the primary, while the analyses based on the PP analysis set will be considered supportive. PoC will be considered to be established if the repeated measures ANCOVA model results in a significant positive average treatment effect of merotocin compared to placebo across the treatment period in the FAS.

Primary Endpoint: Sensitivity/Supportive Analyses

The Safety Committee may choose to reduce the dose in case of any safety concerns. In that case, the analyses will be performed both by combining the merotocin dose groups into one and by using the actual merotocin dose groups separately.

Sensitivity analyses exploring the impact of the missing data assumption on the results of the primary analysis will be performed for the FAS and PP analysis sets. Missing data will be imputed under a MNAR assumption using the pattern-mixture model with control-based pattern imputation.

The sensitivity of the results with respect to choice of the covariance structure will be investigated using more restrictive covariance structures (compound symmetry, Toeplitz, separate compound symmetry for each treatment group, and separate Toeplitz pattern for each treatment group). Nested models will be compared using the likelihood ratio test. In addition, interactions of treatment and gestational age group will be tested in the model with a general covariance structure.

Although the randomization will be stratified by site, it will not be included in the model for the primary analysis because issues may arise when adjusting for a large number of small centers (with respect to the number of randomized subjects). Additionally, common methods, such as pooling small centers together to form one large center, lack scientific justification. To ensure that the trial conclusions are not substantially affected by this exclusion, sensitivity analyses will examine the relationship between the effect of treatment and center. This will be carried out by including center and the center*treatment interaction as factors in the repeated measures ANCOVA model specified for the primary endpoint.

Sensitivity analyses will be performed to assess the relationship between the time of randomization from delivery and the effect of treatment on the volume of MoM produced over Days 1 to 14. This will be carried out by including the time of randomization from delivery and the time of randomization from delivery by treatment interaction in the repeated measures ANCOVA model specified for the primary endpoint.

The above primary analysis will be repeated to examine the consistency of the relationship between treatment and the volume of MoM produced over Days 1 to 14 after having adjusted for additional covariates (age of maternal subject, ethnicity, presence of fetal growth restriction, birth weight, caesarean section, primipara versus multipara, use of antenatal steroids and pre-pregnancy BMI). Each covariate will be added to the model one by one and tested at a two-sided significance level of 20%. In case two or more covariates are significant at the 20% level, a forward selection process will be applied with a threshold for adding effects at a two-sided significance level of 20% to identify the final model.

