3.6.6 Selection of the Trial Population

A high proportion of the mothers of premature infants experience challenges in establishing an adequate milk supply. Due to the prematurity of the infant and the infant's diminished ability to suckle, these mothers are often deprived of the natural stimulus for lactation and may be dependent upon a breast pump. Breast pump dependency means that the pump is the primary driver of milk removal and mammary gland stimulation even though the infant may be able to feed at the breast.³⁰ The stress of having a premature infant may further impede milk production. On the other hand, the potential benefits of MoM in preterm infants are well documented,^{2,31} which is likely to highly motivate mothers of preterm infants to express milk. For benefits to both mothers and infants, there are minimal ethical concerns about requiring a stringent milk expression schedule.

The trial population is women with infants at a high degree of prematurity. A gestational age range of 24 weeks + 0 days to 31 weeks + 6 days was originally chosen. However, by the amendment

(dated 06-04-2022), the window was expanded to 34 weeks + 2 days because many women who deliver infants at this gestational age are breast pump dependent and struggle to achieve an adequate milk supply. The upper limit of the gestational age is chosen to ensure the infants who are primarily breastfeeding at the time of enrollment would not be eligible. More breastfeeding may occur towards the end of the trial period among women who have delivered infants at the upper end of the gestational age range per eligibility criteria; however, that is not necessarily indicative of breast pump independence. Prematurity is one of several reasons for breast pump dependency; however, it is a focus of this early phase trial because of the high proportion of milk supply inadequacy experienced by women with premature birth.

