9.1 Determination of Sample Size

The primary objective of this trial is to evaluate the effect of merotocin on increasing milk production in women with preterm delivery. The comparison is based on the primary endpoint of the volume of MoM produced over Days 1 to 14.

Since neither the onset nor the duration of effect of merotocin is known, the initial sample size calculation is based on a comparison of the time-averaged difference between the merotocin group and the placebo group over Days 1 to 14. A sample size of 100 maternal subjects, allocated equally to each treatment group, will provide roughly 80% power to detect a 50% increase in the volume of MoM produced over Days 1 to 14, compared to placebo.

The primary analysis of the volume of MoM obtained over Days 1 to 14 will be based on a repeated measures ANCOVA. For a given sample size, the power is a function of the assumed (constant) treatment effect and the assumed correlation of observations within subjects. The power for a sample size of 100 maternal subjects equally distributed between the two treatment groups for various combinations of correlation and treatment effect is shown in [Table 7](#). As shown in the table, a sample size of 100 subjects has approximately 80% power to detect a 50% increase in the volume of MoM produced, unless the within subject correlation is greater than 0.8.

Table 7 Power for Various Combinations of Correlation and Treatment Effect

Correlation	Treatment effect ^a (merotocin relative to placebo)		
	30% increase	40% increase	50% increase
0.6	64.2 %	81.1 %	92.3 %
0.7	57.2 %	74.4 %	86.1 %
0.8	52.1 %	66.5 %	80.2 %

^a Assuming 100 subjects will be equally distributed between the two groups, with a uniform 30% drop-out rate in the trial.

The results presented in [Table 7](#) are based on simulations. For each scenario, 1,000 datasets with 100 subjects equally distributed between the 2 treatment groups were generated. In each simulation, 14 observations from a multivariate log-normal distribution were generated for each subject. The means and variances of the multivariate log-normal distribution used to draw samples from, were based on external data received by Ferring. The correlation between the volume of MoM expressed

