9.6.3 Secondary Endpoints

Secondary efficacy endpoints will be analyzed using the FAS and the PP analysis set, whereas secondary safety endpoints will be reported using the safety analysis set.

The time from randomization to the first occurrence of a daily volume of MoM ≥ 500 mL and ≥ 750 mL will be analyzed by fitting a discrete time survival model adjusted for gestational age group, as well as the baseline volume of MoM.

The proportion of maternal subjects producing at least 500 mL and 750 mL of MoM over Days 1 to 14 will be analyzed by repeated logistic regression adjusted for treatment day, treatment-by-day interaction and gestational age group.

The volume of MoM produced over Days 15 to 17 will be compared between treatment groups using a repeated measures ANCOVA model adjusting for the volume of MoM produced on Day 14.

Volume of MoM fed to the infant over Days 1 to 14 and volume of formula/donor milk fed to the infant over Days 1 to 14 will be analyzed and presented using an ANCOVA approach similar to the one used for the primary endpoint but gestational age will be adjusted for as a continuous covariate.

The proportion of subjects with quantifiable amount of merotocin in the milk will be summarized for the merotocin group.

Infant body weight will be summarized by treatment day, treatment group and gestational age measured in weeks, together with change from baseline values.

Maternal subject TEAEs will be summarized by treatment group, including separate summaries by intensity. All infant AEs will be summarized by treatment group, again including separate summaries by intensity. Further details are provided in Section 9.8.2.

Routine safety laboratory parameters of maternal subjects will be summarized by time point and treatment group, together with change from baseline values. For each laboratory parameter, a summary table will be prepared displaying the proportion of maternal subjects who have at least one markedly abnormal value. Markedly abnormal criteria for the safety laboratory parameters will

be specified in the SAP.

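### The primary model adjusts for gestational age only as below or above 27 weeks, so any age gradient in milk volume within the wide upper class is left in the residual; this is a small efficiency loss, not a validity problem

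*Combined protocol and SAP*

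**What the plan says.** Section 9.6.2 fits daily milk volume on baseline volume, treatment, day, "treatment-by-day interaction, and gestational age group", with the age groups cut at 27 weeks. Section 4.2.2 uses the same cut, together with site, to stratify randomisation.

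Section 3.6.6 gives an original upper age limit of 31+6 and reports that by amendment "the window was expanded to 34 weeks + 2 days". The cut in the current text is 27 weeks; no reason for it is given.

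No analysis of the primary endpoint uses continuous age. Section 9.6.2 tests treatment by age group. It also lists extra covariates, which include birth weight and fetal growth restriction but not gestational age, and which enter through a 20% significance screen. In Section 9.6.3, for the volumes of mother's milk and of formula or donor milk fed to the infant, "gestational age will be adjusted for as a continuous covariate". Section 6.2 records gestational age at screening for every woman.

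**The concern.** A two-level factor treats a delivery at 27+0 and one at 34+2 as the same with respect to age. If milk volume changes with age across those weeks beyond what baseline volume captures, that variation widens the confidence interval of the one test on which proof of concept depends. Stratification balances the arms on the two classes, not on age within the upper class, so a chance difference there goes unadjusted.

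Some relevance of age is plausible. The sponsor chose it as a stratification factor and a model term, and Section 1.1 describes the breast after preterm delivery as not fully prepared for lactation. The term is already recorded, so any precision it offers is nearly free.

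**Working it through.** **Inputs from the protocol**
- Test (Section 9.6.1): "All statistical tests will be performed using a two-sided test at a 5% significance level", so z = 1.960.
- Power (Section 9.1): "A sample size of 100 maternal subjects, allocated equally to each treatment group, will provide roughly 80% power". The effect behind that figure is a gain of 50% over placebo, and the claim carries the condition "unless the within subject correlation is greater than 0.8". Table 7 gives 80.2% at correlation 0.8, "with a uniform 30% drop-out rate in the trial".
- Age range (Section 4.1.1): 24+0 to 34+2. Counting the whole last day this is 24 to 34.43 weeks, a width of 10.43. The lower class takes 3 weeks, a fraction c = 3/10.43 = 0.288, and the upper class 7.43.

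**Not in the documents, so assumed**
- The distribution of age over the range.
- R², the share of variance in milk volume, after baseline volume, that a linear age effect explains. Values of 0 to 0.10 are shown.

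**Step 1: the plan's own figure.** Table 7 comes from simulations whose means and variances are not printed. A normal approximation on the 14-day mean, with SD multiplied by √((1+13ρ)/14), was solved for the SD from the 80.2% cell. It was tried with 50 or 35 women per arm and three variance assumptions. Only 1 or 2 of the other 8 cells then came within 2 points. The table can be neither reproduced nor called wrong; 80.2% serves below only as an anchor for the planned model.

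**Step 2: how much of a linear age effect the cut keeps.** This is r², the squared correlation between age and the below-27 indicator. Suppose the share of women below a fraction x of the range is x^k (k = 1 is uniform; larger k means later deliveries). Then p = c^k are below 27 weeks, and r² = [p/(1−p)] × (1−c)² × k(k+2).
- Uniform, k = 1: p = 0.288 and r² = 3 × 0.288 × 0.712 = 0.615.
- 15% below 27 weeks, k = ln 0.15/ln 0.288 = 1.52: 0.1765 × 0.507 × 1.52 × 3.52 = 0.48.
- 10% below, k = 1.85: 0.1111 × 0.507 × 1.85 × 3.85 = 0.40.
- k = 2 and k = 3 (8% and 2% below): 0.37 and 0.19.

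For the former range (c = 3/8), k = 1, 2 and 3 give 0.70, 0.51 and 0.33, so widening the range reduced what the cut captures.

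**Step 3: power.** Replacing the captured share by the full linear effect multiplies residual variance by v = (1−R²)/(1−r²R²). Power is Φ(2.809/√v − 1.960), where 2.809 = 1.960 + 0.849 returns 80.2% at v = 1. For example, with R² = 0.05 and uniform age, v = 0.95/(1 − 0.615 × 0.05) = 0.980, and Φ(2.809/0.990 − 1.960) = Φ(0.877) = 81.0%.

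| R² | k = 1 (r² 0.615) | k = 2 (r² 0.367) | k = 3 (r² 0.185) |
|---|---|---|---|
| 0 | 80.2% | 80.2% | 80.2% |
| 0.02 | 80.5% | 80.7% | 80.8% |
| 0.05 | 81.0% | 81.5% | 81.8% |
| 0.10 | 81.8% | 82.8% | 83.5% |

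The number giving the same precision is 100v: 96-98 women at R² = 0.05 and 92-96 at 0.10, instead of 100.

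**Step 4: chance imbalance.** With uniform age, about 0.71 × 50 ≈ 35 women per arm fall in the upper class. The SD of age there is 7.43/√12 = 2.1 weeks. The arm difference in mean age has standard error 2.1 × √(2/35) = 0.5 week, so gaps of up to about 1 week are ordinary.

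**Step 5: simulation check.** 4,000 trials per setting were simulated: ANCOVA on the subject mean, 100 women, uniform age, stratified at 27 weeks, no baseline-volume term. Linear age was put in place of the factor rather than beside it. Type I error was 4.4-4.9% with either coding. Power was 80.5% with the factor against 80.9% with linear age at R² = 0.05, and 82.3% against 83.6% at R² = 0.10 (Monte Carlo standard error about 0.6 points).

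**The case against.** The best defence is that nothing here is an error. The model adjusts for age as randomisation was stratified, each woman's baseline volume is already in it, and all women enter with less than 200 mL in 24 hours. If age adds nothing after baseline volume, continuous coding gains nothing. The 80.2% anchor is also the lowest of the 50%-increase cells in Table 7; the others are 86.1% and 92.3%. Birth weight and fetal growth restriction in the covariate list narrow the gap, though they do not replace age. All of this stands, and it limits the point to efficiency.

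Several stronger readings are tempting but unsupported:
- **That the test is biased or its error rate inflated.** The stratification factor is in the model, and the simulation shows no inflation.
- **That prognostic information is known to be lost.** No document reports how age within the upper class relates to volume after baseline adjustment. The figures in Section 1.1 (about 48% against 83% with adequate production) compare preterm with term mothers, not ages within the eligible range.
- **That the cut is left over from the narrower range.** Section 3.6.6 gives the former range but not when or why 27 weeks was chosen.
- **That the plan contradicts itself by using continuous age elsewhere.** It does so only for infant intake, as an explicit departure from the primary approach. The maternal production analyses in Section 9.6.3 that adjust for age (time to, and proportion reaching, 500 and 750 mL) use the group. The comparison shows only that the specification is available.
- **That the cut keeps just 27-38% of the age effect when 10-15% of women are below 27 weeks.** A reader could get this by putting p = 0.10-0.15 into 3p(1−p). That formula needs uniform age, which fixes p at 0.29; the rising densities of Step 2 give 40-48%.

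**Conclusion.** The point holds as a minor matter of efficiency. The primary model cannot use any age gradient between 27+0 and 34+2, and no planned analysis of the primary endpoint fills that gap. Under a linear age effect the two-level factor keeps about 62% if age is uniform, and about 40-48% under a power-law rising density with 10-15% of women below 27 weeks.

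The likely gain is about 0.3 to 1.6 points of power for R² of 0.02-0.05 and 1.6 to 3.3 points at 0.10, with none at 0. These figures assume linearity, the age distributions shown, and 80.2% as the power of the planned model. The conclusions of the trial would not be invalid if the model were left as it is.

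**What to change.** Before unblinding, pre-specify gestational age in weeks as an additional continuous covariate in the primary repeated measures ANCOVA. Keep the factor at 27 weeks and leave the randomisation strata unchanged. It is preferable to settle this before the futility analysis in Section 9.9, so that conditional power rests on the same model.

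The primary model is written into the protocol, so this change needs an amendment under Section 12.1. If the sponsor prefers not to alter that model, the minimum is a pre-specified sensitivity analysis that adds continuous age to it and is not subject to the 20% screen. This can go in the SAP, which Section 9 says will be available before the blind is broken.

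No new data are needed. The cost is one degree of freedom and an assumed linear age effect that is correlated with the stratum factor.
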